#### **11.1.2.4.5. Expedited Reporting by the Sponsor to a Regulatory Health Authority**

The Sponsor will manage the expedited reporting of relevant safety information to concerned health authorities, competent authorities, and IRBs/IECs in accordance with local laws and regulations.

#### **11.1.2.4.6. Safety Notifications by the Sponsor to the Investigator**

Investigators will receive prompt notification of any suspected adverse drug reaction that is both serious and unexpected, or any finding that suggests a significant risk for patients, in accordance with local laws and regulations. The Investigator will promptly inform his/her IRB/IEC of the notification and insert the notification in the Investigator's Regulatory Binder in accordance with local regulations.

### **11.2. Assessment of Efficacy**

Tumor response will be determined by the investigator according to RECIST v1.1 and iRECIST. Tumor response according to iRECIST will be used for treatment decision-making and other supporting disease-specific efficacy measurements. Tumor evaluations during treatment period in Arm 1 will be performed at Weeks 4, 12, 18, and 24, followed by every 12 weeks until disease progression. Tumor evaluations during treatment period in Arm 2 will be at Weeks 6, 12, 18, and 24, followed by every 12 weeks until disease progression.

Tumor evaluations during the treatment period in Phase 2 will be at Weeks 6, 12, 18, and 24, followed by every 12 weeks until disease progression or the completion of 35 treatment cycles. Patients who discontinue study treatment without experiencing iCPD will continue to undergo tumor assessment according to the SOA until up to 24 months after the last dose of study drug, the start of new anticancer therapy, iCPD per iRECIST, death, loss to follow-up, withdrawal of consent, or the end of the study, whichever occurs first.

## 12. STATISTICS

### 12.1. Statistical Methods

Detailed methodology for the statistical analyses of the data collected in this study will be documented in the statistical analysis plan (SAP), which will be maintained by [REDACTED]. The SAP may modify the plans outlined in the protocol; however, any major modifications of the primary endpoint definition and/or its analysis will also be reflected in a protocol amendment.

In general, all efficacy and safety endpoints will be analyzed using descriptive statistics (n, mean, standard deviation, median, and ranges for continuous variables; frequencies and percentages for categorical variables).

All deviations related to conduct of the study, patient management, or patient assessment will be identified, evaluated, and closed before database lock and will be described in the final CSR. Protocol deviations are not allowed for inclusion or exclusion criteria.

#### 12.1.1. Determination of Sample Size

##### 12.1.1.1. Dose-search Part (Phase 1b)

In the dose-search part of the study, there will be 6 to 12 patients for each arm (up to a total of 24 patients). If a patient is terminated before having any evaluable data, the patient will be replaced until the planned sample size is reached.

In the enrichment cohort, 10 patients will be enrolled to help evaluate the preliminary antitumor activity and the safety profile of DSP-7888 Dosing Emulsion.

If anti-tumor activities are observed in any tumor type, additional patients may be enrolled for further assessment.

##### 12.1.1.2. Dose-Expansion Part (Phase 2)

There is no formal hypothesis testing for the Phase 2 cohort. Approximately 40 eligible PROC patients are expected to be enrolled in the Phase 2 dose expansion part of the study. A Bayesian decision-making framework will be employed to quantify whether proof of concept (POC) can be established based on the overall response rate (ORR) by Week 24 from the final analysis for overall population and/or CPS < 10 subpopulation. The POC is established at the final analysis if either or both of the following two conditions are met:

- In the overall population, 70% credible interval of ORR with 10% in the left tail and 20% in the right tail will be calculated: if lower bound  $\geq 8\%$  and upper bound  $\geq 21\%$  (where 8% is the reference value [Section 4.3.1; Matulonis, 2019]) and 21% is the target value of ORR in the overall population), the study achieve POC.
- In the CPS < 10 subpopulation, 50% credible interval of ORR with 20% in the left tail and 30% in the right tail will be calculated: if lower bound  $\geq 5\%$  and upper bound  $\geq 15\%$  (where 5% is the reference value [Section 4.3.1; Matulonis, 2019] and 15% is the target value of ORR in CPS < 10 subpopulation), the study achieves POC.

Statistical analysis may be conducted to evaluate the relationship between ORR and the PD-L1 level and/or WT1 using statistical methods, such as ROC curve or contingency table.

In Phase 2 of the study, approximately 40 patients will be enrolled. Additional patients may be enrolled to further assess anti-tumor activities in the subgroups of interest. However, the total sample size of Phase 2 cannot exceed 60 patients. In total, approximately 64-84 patients will be enrolled in the study.

### **12.1.2. Analysis Datasets**

#### **12.1.2.1. Full Analysis Set**

The Full Analysis Set (FAS) consists of all patients who receive at least 1 full or partial dose of study treatment (DSP-7888 Dosing Emulsion, nivolumab, or pembrolizumab). Patients will be classified according to the treatment assigned (dose level and schedule).

Patients who were screened but never started treatment will be listed but not included in the FAS. Screening failures will not be included in any of the summary tables.

#### **12.1.2.2. Safety Set**

The Safety Set (SS) consists of all patients who receive at least 1 full or partial dose of study treatment (DSP-7888 Dosing Emulsion, nivolumab, or pembrolizumab). Patients will be classified according to the treatment received (dose level and schedule), where treatment received is defined as the assigned treatment if the patients took at least 1 dose of that treatment or the first treatment received if the assigned treatment was never received.

#### **12.1.2.3. Dose-Determining Set**

The DDS includes all patients from the FAS (Phase 1b, dose-search part only) who met the minimum exposure criterion and had sufficient safety evaluations or experienced a DLT during in the first 2 cycles of treatment.

A patient is considered to have met the minimum exposure criterion if he/she received at least 50% of the planned doses of DSP-7888 Dosing Emulsion ( $\geq 3$  doses) and nivolumab/pembrolizumab ( $\geq 1$  dose) during the first 2 cycles.

Patients who do not experience a DLT during the first 2 cycles are considered to have sufficient safety evaluations if they have been observed for 2 cycles after the first dose, and are considered by both the Sponsor and investigators to have enough safety data to conclude that a DLT did not occur.

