### 6.1.1. Phase 1b

#### 6.1.2. Dose Search Part

After providing written informed consent, patients will undergo screening assessments, which will include a careful review of each patient's medical history.

Patients will be administered doses of DSP-7888 Dosing Emulsion intradermally in both arms of the study (Arm 1 and Arm 2). Arm 1 will include patients with indications approved by the Health Authorities for treatment with nivolumab: advanced melanoma, non-small cell lung cancer (NSCLC), RCC, urothelial carcinoma, head and neck squamous cell carcinoma (HNSCC), hepatocellular carcinoma (HCC), and microsatellite instability-high or mismatch repair-deficient (MSI H/dMMR) colorectal cancer. Arm 2 will include patients with indications approved by the Health Authorities for treatment with pembrolizumab: melanoma, NSCLC, HNSCC, urothelial carcinoma, MSI-H/dMMR cancer, gastric cancer or gastroesophageal junction adenocarcinoma, and cervical cancer (Figure 3).

In the Phase 1b dose search part of the study, during the Arm 1 induction phase (4 weeks), DSP-7888 Dosing Emulsion will be administered once weekly for 4 weeks, with nivolumab administered every other week. In the subsequent Arm 1 maintenance phase, DSP-7888 Dosing Emulsion will be administered once every 2 weeks with nivolumab until a discontinuation criterion is met. Arm 2 will include patients with indications approved by the Health Authorities for treatment with pembrolizumab: melanoma, NSCLC, HNSCC, urothelial carcinoma, MSIH/-dMMR cancer, gastric cancer or gastroesophageal junction adenocarcinoma, and cervical cancer. During the Arm 2 induction phase (6 weeks), DSP-7888 Dosing Emulsion will be administered once weekly for 6 weeks, with pembrolizumab administered once every 3 weeks. In the subsequent Arm 2 maintenance phase, DSP 7888 Dosing Emulsion will be administered once every 3 weeks with pembrolizumab until a discontinuation criterion is met.

Both programmed cell death-1 (PD-1) inhibitors (nivolumab and pembrolizumab) will be administered in the approved dose and schedule starting on Day 1 of the study. Study sites will not be limited to any arm of the study, and each arm will investigate the recommended dose in parallel.

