#### 6.4. Dose-limiting Toxicities (Phase 1b Dose Search Part Only)

A dose-limiting toxicity (DLT) is defined by the occurrence of 1 of the toxicities defined below, occurring during the first 28 days of Arm 1 (DSP-7888 Dosing Emulsion induction phase in combination with nivolumab; Arm 1) and the first 42 days of Arm 2 (DSP-7888 Dosing Emulsion induction phase in combination with pembrolizumab; Arm 2).

Evaluable patients are defined per Dose-Determining Set (DDS), as defined in [Section 12.1.2.3](#). Patients who discontinue before meeting the DDS criteria may be replaced to fully evaluate a given dose level. The criteria for the determination of DLT will apply to a given administration schedule independently.

No inpatient dose escalation/de-escalation is allowed during the DLT evaluation period.

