3.2. Safety Set

The Safety Set (SS) consists of all patients who receive at least 1 full or partial dose of study treatment (DSP-7888 Dosing Emulsion, nivolumab, or pembrolizumab). Patients will be classified according to the treatment received (dose level and schedule), where treatment received is defined as the actual treatment if the patients took at least 1 dose of that treatment or the first treatment received if the assigned treatment was never received.

Safety analysis set will be used for all safety related analyses such as AE, concomitant medication, laboratory tests, and vital signs and drug exposure evaluation.

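### The DLT-evaluability rule equates 50% of planned DSP-7888 doses with 3 doses, which is 75% in Arm 1, and SAP v3.0 no longer fixes the denominator for DLT incidence

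*Protocol*

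**What the plan says.** Protocol Section 12.1.2.3 defines the DDS for the Phase 1b dose-search part only. A patient enters by having a DLT in the first two cycles, or by meeting a minimum exposure criterion and having sufficient safety evaluations. The exposure criterion is that the patient "received at least 50% of the planned doses of DSP-7888 Dosing Emulsion", and the same sentence turns the percentage into a count, "DSP-7888 Dosing Emulsion ( $\geq 3$ doses) and nivolumab/pembrolizumab", with at least 1 dose required of the PD-1 inhibitor. One count serves both arms. Sufficient safety evaluation means observation for two cycles, plus agreement by the sponsor and the investigators that no DLT occurred.

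The dose-search regimen is in Protocol Section 6.1.2. In Arm 1, "DSP-7888 Dosing Emulsion will be administered once weekly for 4 weeks, with nivolumab administered every other week". In Arm 2, "DSP-7888 Dosing Emulsion will be administered once weekly for 6 weeks, with pembrolizumab administered once every 3 weeks". Cycles are 14 days in Arm 1 (Table 7) and 21 days in Arm 2 (Table 8). Section 6.4 sets DLT windows of 28 and 42 days and defines evaluable patients by the DDS.

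Replacement is covered twice. Section 6.4: "Patients who discontinue before meeting the DDS criteria may be replaced to fully evaluate a given dose level". Section 12.1.1.1: "If a patient is terminated before having any evaluable data, the patient will be replaced until the planned sample size is reached".

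SAP v3.0 keeps DLT incidence as a Phase 1b primary endpoint (Section 1.2.1.1) and still has DDS in its abbreviation list, but Section 3 defines only the Full Analysis Set and the Safety Set. Section 3.2 adds: "Safety analysis set will be used for all safety related analyses such as AE", and goes on to name concomitant medication, laboratory tests, vital signs and exposure. SAP Section 5.3 repeats the recommended-dose rule of Protocol Section 6.5, which speaks of 6 enrolled patients in one sentence and of DLT-eligible patients in another.

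**The concern.** The percentage and the count are offered as the same threshold. They agree only if 6 doses are planned, which is true of one arm. In the other arm the sentence sets two thresholds, and one kind of patient falls between them.

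The DDS defines who is evaluable for the DLT endpoint and who counts toward the rule of 0 or 1 DLT in 6. If membership depends on which half of a sentence is read, the Arm 1 denominator can be settled after the data are known. The SAP is where that should be closed. Instead it drops the set, leaves the Safety Set as the only safety population, and specifies no DLT table or denominator in Sections 5.4.1 to 5.4.4. Since v3.0 reduces the final report to safety, DLT incidence is one of the few primary results left to report.

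**Working it through.** **Planned doses in the first two cycles, dose-search schedule** (Protocol Section 6.1.2, Tables 7 and 8 for cycle length, and the dosing days in SAP Figure 1)

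- Arm 2: 2 × 21 = 42 days. DSP-7888 on Days 1, 8, 15, 22, 29 and 36 = 6 doses.
- Arm 1: 2 × 14 = 28 days. DSP-7888 on Days 1, 8, 15 and 22 = 4 doses.

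**Reproducing the plan's figure** (count = 0.5 × planned doses)

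- Arm 2: 0.5 × 6 = 3. The stated 3 is reproduced.
- Arm 1: 0.5 × 4 = 2. The stated 3 is not reproduced; 3/4 = 75%.
- PD-1 inhibitor: 2 planned doses in each arm (Days 1 and 15, or Days 1 and 22), 0.5 × 2 = 1. The stated 1 is reproduced.

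**Could the later schedule explain the 3?** Under Amendment 5 each arm has 4 DSP-7888 doses in its first two cycles (Days 1, 8, 15 and 22), so 50% is 2 in both. Nivolumab would start on Day 29, after the 28-day window, so its minimum of 1 dose could not be met. The rule belongs to the earlier schedule, and the 3 fits Arm 2 of that schedule only.

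**Who is affected in Arm 1** (exposure and observation together, or a DLT alone, taken as the routes into the DDS; at least 1 nivolumab dose and sponsor and investigator agreement assumed where relevant)

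| Arm 1 patient | 50% read literally | At least 3 read literally |
|---|---|---|
| DLT in the first two cycles | in | in |
| No DLT, leaves before 28 days | out | out |
| No DLT, 28 days observed, 3 or 4 doses | in | in |
| No DLT, 28 days observed, exactly 2 doses | **in** | **out** |
| No DLT, 0 or 1 dose | out | out |

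Only the fourth row changes.

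**Size.** Protocol Section 4.3.2 reports 7 Arm 1 patients as of 16 Dec 2019. Assume that exactly one was in the fourth row; the DDS then holds 7 or 6. The DLT count is not given, so a range is shown:

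- 0 DLTs: 0/7 = 0/6 = 0%.
- 1 DLT: 1/7 = 14.3% or 1/6 = 16.7%, a gap of 2.4 points.
- 2 DLTs: 2/7 = 28.6% or 2/6 = 33.3%, a gap of 4.8 points.

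The same arithmetic applies if the one patient is instead an early leaver, and the choice is between Safety Set (7) and DDS (6). With 6 enrolled rather than 7, one fourth-row patient leaves 6 or 5 evaluable, and 5 is short of the 6 for which the rule in Section 6.5 is written.

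**Which denominator?** Protocol Section 6.4 points to the DDS. Protocol Section 12.1.5.2 promises the number evaluable for dose search beside the number with DLTs. SAP Section 5.3 says DLT-eligible, without defining it. SAP Section 3.2 gives safety analyses to the Safety Set, which includes anyone with a single partial dose. No SAP section connects these.

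**The case against.** The strongest reply is that nothing is left to decide. Protocol Section 6.1.2 says the dose-search part is complete with no further enrolment, the enrichment cohort is outside the DLT endpoint, and Phase 2 already runs at 10.5 mg. The two-cycle observation requirement also narrows the gap to one unusual patient, and no document shows that such a patient existed. The SAP is to be read with the protocol, which does define the DDS, and SAP Section 3.2 does not name DLTs. All of this stands. It limits the point to reporting and the audit trail, but it does not make 3 equal to half of 4 or put a denominator into the SAP.

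A reader might infer more, in four ways that the documents do not support.

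- *That a patient who stops after two doses and leaves is the problem case.* Leaving before 28 days fails the observation requirement under either count.
- *That the replacement rules contradict each other.* Section 6.4 permits replacement of anyone who discontinues before meeting the DDS criteria. Section 12.1.1.1 requires it for the narrower case of no evaluable data, and does not say that this is the only case. Both can be followed. The difference in wording is a minor inconsistency.
- *That the SAP puts early leavers and their replacements together in the DLT denominator.* It does not say so; SAP Section 5.3 speaks of DLT-eligible patients. The denominator is unstated, not wrongly stated.
- *That the seventh Arm 1 patient was a replacement, or that the recommended dose would have differed.* Six to 12 patients per arm were planned, so a seventh needs no such explanation. The dose decision was a count rule reviewed case by case by the Safety Review Committee, and a Safety Set percentage would not have entered it.

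**Conclusion.** The stated equivalence is wrong for Arm 1: 50% of 4 planned doses is 2, and 3 doses is 75%, a difference of 25 percentage points of planned exposure. This rests only on the protocol's own schedule. Separately, SAP v3.0 retains DLT incidence as a primary endpoint without defining the set on which it is calculated.

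The practical size is small. It needs an Arm 1 patient with exactly 2 DSP-7888 doses, at least 1 nivolumab dose, 28 days of observation and no DLT, or, for the choice between DDS and Safety Set, any treated dose-search patient outside the DDS. With one such patient among 7 and one DLT, the reported rate moves by 2.4 points; with no DLTs it does not move at all. Both the patient and the DLT count are assumptions. The sponsor should make the correction because it settles how a primary endpoint is reported, not because it casts doubt on the dose chosen.

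**What to change.** 1. In Protocol Section 12.1.2.3, give the percentage and the count separately for each arm so that they agree, and state which criterion was actually applied at the dose-search review. Because the Arm 1 data already exist, the choice should follow what was applied then, not be made afresh.
2. In SAP Section 3, restore the DDS and name it as the denominator for DLT incidence. In SAP Section 5.3, tie DLT-eligible to it.
3. List dose-search patients who are in the Safety Set but outside the DDS, with the reason for each. If any Arm 1 patient had exactly 2 DSP-7888 doses, report DLT incidence both with and without that patient.
4. Optionally, align the replacement wording in Sections 6.4 and 12.1.1.1 for the record. It would no longer change who is replaced.

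The cost is a few lines of wording and one listing. The DLT percentage may look slightly less favourable, since the DDS cannot be larger than the dose-search Safety Set.

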#### **12.1.2.4. Efficacy Set**

The Efficacy Set (ES) includes all patients from the FAS who have responded to treatment (CR/PR), assessed as progressed on treatment without regard to length of treatment, or have been on treatment for 6 months or more without regard to tumor response status.

